- Proportion of 1-point composite responders as defined by responses in the quadrant treated in study EN3835-201 who either maintained response, lost response but did not return to the baseline of study EN3835-201, or returned to the baseline of study EN3835-201.
- Proportion of 2-point CR-PCSS responders as defined by responses in the quadrant treated in study EN3835-201 who either maintained response, lost response but did not return to the baseline of study EN3835-201, or returned to the baseline of study EN3835-201.
- Proportion of 1-point CR-PCSS responders as defined by responses in the quadrant treated in study EN3835-201 who either maintained response, lost response but did not return to the baseline of study EN3835-201, or returned to the baseline of study EN3835-201.
- Proportion of 2-point PR-PCSS responders as defined by responses in the quadrant treated in study EN3835-201 who either maintained response, lost response but did not return to the baseline of study EN3835-201, or returned to the baseline of study EN3835-201.
- Proportion of 1-point PR-PCSS responders as defined by responses in the quadrant treated in study EN3835-201 who either maintained response, lost response but did not return to the baseline of study EN3835-201, or returned to the baseline of study EN3835-201.

EN3835-202 Protocol Amendment 2

- Duration of response as defined by the time from onset of change from baseline of PR-PCSS and CR-PCSS in the quadrant treated in study EN3835-201 until the time that the treated quadrant returned to the baseline PR-PCSS and CR-PCSS ratings from study EN3835-201.
- CR-PCSS change from the study EN3835-201 baseline at Day 71 of study EN3835-201, and Days 90, 180, 270, and 360/end of study of the current study (EN3835-202).
- PR-PCSS change from the study EN3835-201 baseline at Day 71 of study EN3835-201, and Days 90, 180, 270, and 360/end of study of the current study (EN3835-202).
- Hexsel CSS total score changed from the study EN3835-201 baseline at Day 71 of study EN3835-201 and Day 360/end of study of the current study (EN3835-202).
- Proportion of responses at each level of the I-GAIS (Day 360/end of study):
 - Proportion of Investigator global responders defined as subjects with a response of 1 (improved) or better in the Investigator GAIS assessment
 - Change in I-GAIS assessment from Day 71 of study EN3835-201 and Day 360/end of study of the current study (EN3835-202)

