2. ANALYSIS POPULATIONS AND PHASES

The following populations will be considered in the statistical analysis of the study:

- Observation Population: The Observation population includes all subjects rolled over from study EN3835-201. The cellulite assessment evaluations and safety analyses on data collected during observation phase will be performed using this population.
- Safety Population: The Safety population will include all subjects who receive at least 1 dose of EN3835 in the current study. All safety analyses for the treatment phase will be performed using this population. For by region summaries, safety population is considered within each treatment course.
- Effectiveness Population: The Effectiveness population includes all safety subjects who have a baseline and at least 1 post-baseline assessment on both the CR-PCSS and PR-PCSS on the quadrant selected for treatment in the current study. All analysis of effectiveness for the treatment phase will be based on this population. For by region summaries, effectiveness population is considered within each treatment course.
- Durability Population: This population is defined as all active responders who have both CR-PCSS and PR-PCSS at 180 days or above. The active responders are subjects treated with EN3835 with improvements of at least 1 level on each

scale (CR-PCSS and PR-PCSS) at Day 71 visit compared to the baseline. Analysis of durability of treatment effect will be performed using this population.

- Durability Population for Double-blind Treated Subjects: This population is defined as all subjects in the durability population who showed an improvement of at least 1 level on each scale (CR-PCSS and PR-PCSS) at Day 71 visit compared to the baseline for the quadrant treated with EN3835 in double-blind study EN3835-201.
- Durability Population for Open-label Treated Subjects: This population is defined as all subjects in the durability population who showed an improvement of at least 1 level on each scale (CR-PCSS and PR-PCSS) at Day 71 visit compared to the baseline for the quadrant treated with EN3835 in the open-label study EN3835-202 study, who did not have the same quadrant treated with EN3835 in double-blind study EN3835-201. For by region summaries, this population is considered within each treatment course.

The following 2 phases will be summarized in the statistical analysis of the study:

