3. STATISTICAL METHODS AND CONSIDERATIONS

3.1. Descriptive Statistics

All analysis results will be presented in summary table using appropriate descriptive statistics, unless otherwise stated. The statistics include the number (count) and percentage for all categorical variables. The denominator will be based on the number of subjects in each column group in the summary table, unless otherwise stated. All continuous variables will be summarized with observed count, mean, standard deviation, median, minimum, and maximum value.

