6.3. Durability of Treatment Effect

The durability of treatment effect will be accessed based on the longitudinal responses of cellulites assessments of CR-PCSS and PR-PCSS. The number and percentage of responders at each level (ie, 1 level or 2 levels improvements) for CR-PCSS, PR-PCSS and their combinations (ie, composite score, 1 level or 2 levels improvements for both scores) associated with treated quadrants will be summarized by study day. The treatment failure is defined as active responders whose CR-PCSS and PR-PCSS return to the baseline or worse in an EN3835-treated quadrant during a certain follow-up period. The number and percentage will be summarized by study day, ie, Day 180, Day 360, Day 540, and Day 720.

Since there are 2 groups of responders, one group was subjects who were treated with EN3835 in the double-blind EN3835-201 study and followed up in the current EN3835-202 study up to 2 years. The durability analysis described above for this group will be based on the durability population in double-blind treated subjects. The other group will be subjects who will be treated with EN3835 and then followed up to 1 year in the current EN3835-202 study. The durability analysis for this group will be based on the durability population in open-label treated subjects.

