8. HANDLING OF MISSING DATA

8.1. Handling Missing Data on Efficacy Variable

Subjects may have missing data on observational visits at Day 90, Day 180, Day 270, Day 360, and some long-term durability visits, Day 450, Day 540, Day 630 and Day 720. The backward imputation method will be utilized for the values of CR-PCSS and PR-PCSS. For instance, if a subject missed Day 90, Day 180 visits, but he/she has values at Day 270. Then the values at Day 270 will be imputed for the values at Day 180, and Day 90 visits.

No imputation will be applied to other cellulite assessments

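### Responders lost after Day 180 stay in the durability denominator but cannot count as failures, so late treatment failure is understated

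*Combined protocol and SAP*

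**What the plan says.** SAP section 2 calls EN3835-treated subjects active responders if they improve by at least 1 level on both CR-PCSS and PR-PCSS at Day 71. It then narrows the group: "This population is defined as all active responders who have both CR-PCSS and PR-PCSS at 180 days or above". It adds: "Analysis of durability of treatment effect will be performed using this population".

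SAP section 3.1 sets the general denominator: "The denominator will be based on the number of subjects in each column group in the summary table, unless otherwise stated".

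SAP section 6.3 defines the failure outcome: "The treatment failure is defined as active responders whose CR-PCSS and PR-PCSS return to the baseline or worse in an EN3835-treated quadrant", during a follow-up period that it does not specify. On reporting it says: "The number and percentage will be summarized by study day, ie, Day 180, Day 360, Day 540, and Day 720". It names no denominator and no at-risk or censoring rule. It expects up to 2 years of follow-up for women treated in EN3835-201 and up to 1 year for quadrants treated in EN3835-202.

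SAP section 8.1 gives the missing-data rule: "The backward imputation method will be utilized for the values of CR-PCSS and PR-PCSS". Its example carries a Day 270 value back to Days 180 and 90.

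SAP Table 4 schedules Days 450, 540, 630 and 720. It has its own informed-consent row at Day 450, applies to those participating, and lets the last visit be Day 720 or end of study/early termination.

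**The concern.** A failure needs a pair of scores. One pair at Day 180 is enough to enter the durability population and, on the default denominator, to stay in N through Day 720. A woman not seen again has no later value to carry back, so her Day 540 and Day 720 entries stay empty. She remains in the denominator and cannot enter the numerator. The failure percentage then falls as attrition rises, whatever the drug does.

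Durability over 12 months and durability beyond 12 months are two of the secondary objectives in SAP section 1.3.2, and section 6.3 is the analysis written for them. An understated failure rate would make the effect look longer-lasting than the data show.

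**Working it through.** **Figures in the documents.** The plan states no responder rate, failure rate or loss rate for durability, so there is no durability figure to reproduce. The only sample-size figure with inputs is enrolment in Protocol Amendment 2, section 17.1: 0.95 × 350 = 332.5, rounded up to 333. It reproduces and is not in dispute.

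**Assumptions.** All rates below are assumed. Take 100 women in the durability population. Let F be true cumulative failure and m the proportion without data by that visit. Loss is permanent and independent of failure.

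**Formulas.**
- Cumulative count over full N: sum over visits of (increase in F) × (1 − m)
- At-visit count over full N: F × (1 − m)
- Kaplan-Meier: at risk = (1 − previous F) × (1 − m); survival is multiplied by (1 − events / at risk) at each visit

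**Main example.** F = 10, 20, 30, 40% and m = 0, 10, 40, 50% at Days 180, 360, 540, 720.

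| Day | New failures seen | Cumulative / full N | At visit / full N | At risk | Kaplan-Meier failure |
|---|---|---|---|---|---|
| 180 | 10 × 1.0 = 10 | 10% | 10% | 100 | 10% |
| 360 | 10 × 0.9 = 9 | 19% | 20 × 0.9 = 18% | 90 × 0.9 = 81 | 1 − 0.9 × (1 − 9/81) = 20% |
| 540 | 10 × 0.6 = 6 | 25% | 30 × 0.6 = 18% | 80 × 0.6 = 48 | 1 − 0.8 × (1 − 6/48) = 30% |
| 720 | 10 × 0.5 = 5 | 30% | 40 × 0.5 = 20% | 70 × 0.5 = 35 | 1 − 0.7 × (1 − 5/35) = 40% |

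Counting every missing woman as failed gives an upper bound at Day 720 of 100 − 60 × 0.5 = 70%.

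**Range at Day 720.** Each cell is cumulative / at-visit over full N. True failure rises in equal steps to the value shown. Missing data run 0/10/20/30%, 0/10/40/50% or 0/20/60/70% over the four visits.

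| True failure | 30% missing | 50% missing | 70% missing |
|---|---|---|---|
| 20% | 17 / 14% | 15 / 10% | 12.5 / 6% |
| 40% | 34 / 28% | 30 / 20% | 25 / 12% |
| 60% | 51 / 42% | 45 / 30% | 37.5 / 18% |

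With no missing data, every method returns the true value.

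**Women with no scores at 180 days or later.** They leave numerator and denominator together. If a fraction e is excluded with failure q, and those kept have failure p, failure in all responders is (1 − e)p + eq. With e = 20% and p = 40%, this is 0.32 + 0.02 = 34% if q = 10%, and 0.32 + 0.12 = 44% if q = 60%. The bias can go either way.

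**Re-treatment.** A quadrant treated with EN3835 in EN3835-201 qualifies for re-treatment only if both scores are at or above its EN3835-201 baseline (SAP Table 3, footnote j). It has then already met the section 6.3 failure criterion. Re-treatment ends that quadrant's observation phase (SAP section 2), but section 6.3 does not say how scores after re-treatment are handled. If they are used, a second course can read as durability of the first. If they are not, a woman re-treated before Day 180 can leave the population after meeting the failure criterion.

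**The case against.** The full-N denominator is inferred from a general default. Column group is not defined for a by-study-day durability table, and no table shell is shown. The table programmer may intend the number assessed. That stands as a limit, but section 3.1 applies unless another denominator is stated, and section 6.3 states none.

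The follow-up-period wording in section 6.3 points to a cumulative count, so the lower at-visit figures rest on the weaker reading. That also stands, and the cumulative figures should be taken as the main result. A reader might infer that reported failure could fall over time. That can happen only on the at-visit reading.

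Backward imputation fills a gap when a later visit exists, so not every missed visit reads as not failed. A woman who misses Day 540 and has failed by Day 630 counts as failed at Day 540. This does nothing for women who never return.

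Four stronger readings are tempting, and the documents do not support them:
- **Women lost before Day 180, or never entering EN3835-202, count as not failed.** They are excluded altogether, and the direction of that selection is not fixed.
- **The responder and failure percentages contradict each other.** Losing response without returning to baseline is an intermediate state, so the two need not sum to 100%. Full N is conservative for the responder percentages.
- **The duration endpoint was dropped without declaration.** Amendment 2, section 17.5.2, does list "Duration of response as defined by the time from onset of change from baseline of PR-PCSS and CR-PCSS". But the SAP has Day 450 to 720 visits and a longer safety objective that Amendment 2 lacks, so it follows a protocol version not shown here.
- **This is the only view of durability.** SAP section 6.2.3 also reports responders by study day for the EN3835-201 quadrant, and the Observation Population has no later-data requirement.

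Finally, the analysis is secondary and descriptive, in an uncontrolled study that puts its emphasis on safety. That bears on severity.

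**Conclusion.** The concern holds for one defined group: Day 71 responders rated at Day 180 or later who then have no further scores. As the SAP is written they stay in the denominator and cannot fail, so treatment failure is understated at later visits. The effect falls mainly on Days 540 and 720 in women treated in EN3835-201. The open-label group is followed for 1 year only, so it is exposed only up to Day 360.

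In the main example the cumulative shortfall is 5 percentage points at Day 540 (25% against 30%) and 10 at Day 720 (30% against 40%). Across the assumed range, the Day 720 cumulative figure runs from 12.5% against a true 20% to 51% against a true 60%. These sizes rest on assumed rates, on loss independent of failure and on the default denominator. With no loss after Day 180 the problem vanishes.

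This should be fixed before the durability tables are produced. It does not threaten the primary safety objective, so it is a should-fix rather than a must-fix.

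**What to change.** - **Population.** Define it as all EN3835-treated quadrants with a composite response of at least 1 level on both scales at Day 71, with no requirement for later data.
- **Analysis.** Estimate time to return to baseline or worse on both scales by an interval-censored (Turnbull) or Kaplan-Meier method. Use observed scores only, without backward imputation, and censor at the last rating of that quadrant.
- **Re-treated quadrants.** Count a quadrant that met the return-to-baseline criterion before re-treatment as a failure of the first course. Do not use its scores after re-treatment for that course.
- **Reporting.** Give cumulative failure with 95% confidence intervals and the number assessed at Days 180, 360, 540 and 720, stopping at Day 360 for the open-label group.
- **Sensitivity.** Add a missing-as-failure analysis, because women whose cellulite returns may be more likely to leave and Kaplan-Meier would not correct for that.

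Dividing by women rated at the visit plus earlier failures is not an adequate substitute. In the main example at Day 720 it gives 30 failures over 30 + 30 = 60, or 50%, against a true 40%.

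The cost is SAP wording and one standard procedure on data already scheduled. Reported failure will look less favourable, and the late intervals will be wide.

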6.2.3. Observation Endpoints

Observational endpoints for treated quadrant in study EN3835-201 include:

- Change from baseline for PR-PCSS
- Proportions of composite responders defined as subjects with an improvement in severity from baseline of at least 2 (or 1) levels of severity in the CR-PCSS and an improvement in severity from baseline of at least 2 (or 1) levels of severity in the PR-PCSS

- Proportion at each level of improvement in the PR-PCSS:
 - Proportion of patient responders defined as subjects with an improvement in severity from baseline of at least 2 levels on the PR-PCSS
 - Proportion of patient responders defined as subjects with an improvement in severity from baseline of at least 1 level on the PR-PCSS
- Change from baseline for CR-PCSS
- Proportion at each level of improvement in the CR-PCSS:
 - Proportion of Investigator responders defined as subjects with an improvement in severity from baseline of at least 2 levels on the CR-PCSS (Investigator rated)
 - Proportion of Investigator responders defined as subjects with an improvement in severity from baseline of at least 1 level on the CR-PCSS (Investigator rated)
- Proportion of responders at each level of the subject satisfaction at Day 360
- Hexsel CSS total score changed from the study EN3835-201 baseline at Day 71 of study EN3835-201 and Day 360 or Day 360 Beyond long-term durability visits.

These endpoints will be summarized by treatment groups assigned in study EN3835-201 and treated region (buttock or thigh) and overall and by study day using appropriate descriptive statistics.

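### SAP 6.3 reports durability only for EN3835 responders, so its retention and failure tables alone cannot separate lasting drug effect from regression to the mean and rating error

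*Combined protocol and SAP*

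**What the plan says.** SAP section 2 builds the Durability Population from active responders: "The active responders are subjects treated with EN3835 with improvements of at least 1 level on each" scale (CR-PCSS and PR-PCSS) at Day 71, with both scores available at 180 days or later. Section 6.3 analyses two groups, both treated with the drug: "one group was subjects who were treated with EN3835 in the double-blind EN3835-201 study" and "The other group will be subjects who will be treated with EN3835" in the current study. For these women it tabulates 1- and 2-level responders by study day, and failures at Days 180, 360, 540 and 720: "The treatment failure is defined as active responders whose CR-PCSS and PR-PCSS return to the baseline or worse in an EN3835-treated quadrant". No retention or failure rate is planned for placebo responders.

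Placebo data enter elsewhere. In section 2, "The Observation population includes all subjects rolled over from study EN3835-201", whichever arm they were in. Section 6.2.3 covers score changes and single-scale and composite responders: "These endpoints will be summarized by treatment groups assigned in study EN3835-201 and treated region (buttock or thigh) and overall and by study day". SAP Table 2 schedules both scales at Days 90, 180, 270 and 360, and its footnote c has the EN3835-201 quadrant photographed for observation-only subjects without regard to arm. SAP Table 4, footnote d, limits the Day 450-720 ratings to quadrants that received active drug in EN3835-201.

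**The concern.** The durability group is selected twice: on a baseline of 3 or 4 on both scales, and on a fall of at least one level on both at Day 71. Part of that fall is baseline overstatement. Later visits are compared with the same overstated baseline, so this part of the response persists with no drug acting. The failure rule adds to it. A woman with one scale back at baseline and the other one level better is neither a composite responder nor a failure.

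Durability is a stated secondary objective (SAP 1.3.2). A low failure percentage from section 6.3, quoted on its own, would be read as lasting drug effect when much of it could arise from selection and rating error. Women randomised to placebo who met the same Day 71 rule are the natural benchmark, and their first follow-up ratings are made while subjects and investigators are still blinded (protocol Amendment 2, 10.1).

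**Working it through.** **The plan's own figure.** No power, precision or response rate is given for durability. The only sample-size figure with inputs is enrolment (protocol 17.1): 0.95 × 350 = 332.5, rounded up to 333, which reproduces. With 1:1 allocation in EN3835-201 (protocol 8.3.1.4), 333 / 2 = 166.5, or about 166 placebo roll-overs. SAP 1.7 says about 350 instead.

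**Definitions.** Let C and P be the CR-PCSS and PR-PCSS ratings, with subscript 0 for baseline.
- Day 71 responder: C ≤ C0 − 1 and P ≤ P0 − 1.
- Retained at a later visit: the same condition at that visit.
- Failed, reading section 6.3 as needing both scales: C ≥ C0 and P ≥ P0.

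**No-effect models.** True severity is constant for each woman. Ratings are true severity plus error, rounded to whole levels and limited to 0-4, and entry needs 3 or more on both scales. There were 2,000,000 simulated women per setting. The documents give no rating-error figures, so every model input is an assumption.
- Model A: mean severity 2.8-3.2, SD 0.6; a fixed personal offset on each scale, SD 0.3; visit noise SD 0.35-0.65; one qualifying visit.
- Model B: as A, but qualifying at two visits, since protocol Table 4 defines the assigned quadrant as scoring 3 or 4 at both screening and Day 1.
- Model C: mean 2.8, SD 0.7; no fixed offset; noise SD 0.4-0.8; a shared shift in ratings after baseline of 0 to −0.5 level.

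| Model | Day 71 responders | Women of 166 | Retained at one later visit | Failed | Not failed |
|---|---|---|---|---|---|
| A | 4-14% | 7-23 | 25-31% | 21-26% | 74-79% |
| B | 3-11% | 5-18 | 23-26% | 25-29% | 71-75% |
| C | 7-37% | 12-61 | 29-55% | 9-26% | 74-91% |

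With no drug effect, 71-91% are not failed. The gap between retained and not failed comes from the middle group. In Model A at mean 2.8 and noise 0.65, 31.0% are retained and 20.9% failed, leaving 100 − 31.0 − 20.9 = 48.1% in neither category.

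**Other readings of the failure rule.** If failure accumulates over two later visits, Model C gives 15-40% failed, so 60-85% not failed. If either scale returning were enough, not failed would equal retained: 23-55% across the models.

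**Precision of a placebo column** (exact 95% intervals): 2 of 7 retained gives 4-71%; 6 of 23 gives 10-48%; 8 of 17 gives 23-72%. Against an assumed 83 active responders (50% of 166.5), with 80% versus 70% retained, power is only 0.17 to 0.26 for 17 to 50 placebo responders.

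**The case against.** The strongest reply is that section 6.2.3 already supplies a control. It reports composite response by EN3835-201 arm and study day in all roll-overs, unselected on response, so shared rating error appears in both columns. This stands. A reader might infer from section 6.3 that the study cannot tell lasting drug effect from rating error at all; through Day 360 the documents do not support that. What section 6.2.3 does not give is the share of Day 71 responders who keep their response, which is what section 6.3 reports as durability.

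A reader might also infer that placebo responders show what the active responders would have retained without EN3835. They do not. Conditioning on Day 71 response breaks the randomisation: placebo responders are selected by noise or spontaneous change, whereas active responders also include women the drug helped.

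Three further points stand.
- Placebo ratings match the active schedule only to Day 360, so two of the four failure time points (Days 540 and 720) have no possible benchmark.
- After unblinding, placebo follow-up is unclear. Protocol 12.1.3.1 speaks of quadrants treated with EN3835, while SAP Table 2, footnote c, covers the EN3835-201 quadrant of any observation-only subject.
- The unblinding date is not given, so few blinded visits may fall at Day 180 or later.

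It is also fair that the durability objective names only actively treated subjects, that protocol 8.6 calls the efficacy assessment uncontrolled, and that the analyses are descriptive. None of this stops a low failure rate being misread. Nor is section 6.3 uninformative: it also tabulates responders by day, and very high retention would stand well above the 23-55% seen in the no-effect models.

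**Conclusion.** The point holds for the section 6.3 tables taken alone. Under the assumed models, roughly 71-91% of responders would be classed as not failed at one later visit with no drug effect, so a high non-failure rate is not by itself evidence of durability. The range rests on assumed rating error, on reading failure as both scales returning to baseline, and on a single later visit. The direction is the same in all three models; the exact percentages should not be quoted as estimates for this trial.

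The placebo benchmark would be small: about 5-23 women in Models A and B, more only if ratings drift downward after baseline as in Model C. It can calibrate the section 6.3 percentages but cannot serve as a randomised comparison, and no reanalysis can supply one beyond Day 360.

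**What to change.** In SAP 6.3:
- Add a descriptive column applying the same responder and failure definitions to EN3835-201 placebo women who were 1-level composite responders at Day 71.
- Run it through Day 360, up to the first EN3835 injection in that quadrant. Under the backward imputation of SAP 8.1, carry no rating made after that injection back into this period.
- Show visits before the EN3835-201 unblinding separately from later ones. Give counts and 95% intervals beside the active responders at the same visits.
- State that the column is a benchmark for rating error and regression to the mean, not a counterfactual or a test, and direct the reader to the by-arm composite response of section 6.2.3 at the same visits.
- Label the Day 450-720 durability results as uncontrolled.

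Reconcile protocol 12.1.3.1 with SAP Table 2, footnote c, so it is clear which placebo quadrants are rated after unblinding.

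The cost is one extra column from ratings already scheduled. The downside is a small group with wide intervals, and possibly few blinded visits at Day 180 or later.
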